6.7.2. Intra-Patient Dose Escalation of Encorafenib

During the Phase 2 part of the study, all patients will begin treatment with standard doses of encorafenib (450 mg QD) plus binimetinib (45 mg BID). Patients who are able to tolerate the standard dose of encorafenib (450 mg QD) plus binimetinib (45 mg BID) during the first 4 weeks of treatment (Cycle 1) should be dose-escalated to 600 mg encorafenib QD plus 45 mg binimetinib BID provided the following criteria are met:

- Must not have experienced a clinically meaningful treatment-related adverse event of CTCAE \geq Grade 2 that based on investigator assessment prohibits escalation.
- Requires no dose reductions during the first 4 weeks (Cycle 1; guidelines for dose reductions are detailed in [Appendix 2](#) for encorafenib and [Appendix 3](#) for binimetinib). However, a single dose interruption of up to 4 days is permitted during Cycle 1. To ensure steady state exposures of encorafenib + binimetinib in patients undergoing intra-patient dose escalation, 7 days of consecutive dosing at the starting doses (450 mg QD encorafenib + 45 mg BID binimetinib) are required prior to the intra-patient escalation (600 mg QD encorafenib + 45 mg BID binimetinib).

Therefore, intra-patient dose escalation should occur on Cycle 2 Day 1 (+ 7 days).

Investigators must confirm patients meet all criteria to qualify for dose escalation. Patients who cannot tolerate 600 mg QD encorafenib plus 45 mg BID binimetinib will be dose reduced to 450 mg QD encorafenib plus 45 mg BID binimetinib. Re-escalation up to 600 mg QD will not be permitted. Additional dose delays or reductions will be permitted for toxicity management as outlined in [Table 8](#).

6.7.3. Renal Changes in Dose Modification

Encorafenib dose reduction will be considered when either of the following criteria are met:

- ACR increase from baseline > 50%.
- Baseline absolute serum creatinine value increases by ≥ 2 grades on more than 1 occasion. If this occurs, obtain a second serum creatinine measurement within 1 week.

If either of the above criteria are met, a 24-hour urine collection will be assessed for protein and creatinine and serum creatinine will be repeated.

All dosing with study treatment will pause if any of the following criteria are met:

- Calculated GFR decrease of $\geq 50\%$ from baseline.
- Creatinine clearance decrease of $\geq 50\%$ from baseline.
- 24-hour urine protein of > 2 g/24 hours.

If any of the criteria for pausing study treatment are met, the site is directed to obtain a renal consult and to discuss whether the patients should continue study treatment with the Sponsor Medical Monitor.

6.8. Criteria for Permanent Discontinuation of Study Treatment

A patient may choose to withdraw from the study treatment at any time or be withdrawn from the study treatment by the Investigator or Sponsor if the patient does not comply with study requirements. If a patient is withdrawn from study treatment, reasonable efforts will be made to determine the reason for withdrawal, and this information will be recorded in the eCRF.

Patients meeting any of the following criteria should discontinue study treatment:

- Withdrawal of consent/assent (no further participation and thus no further protected health information may be collected).
Note: Patients may choose to discontinue study treatment and remain in the study to be followed for progression and survival. Patients who indicate they wish to withdraw consent should be carefully assessed regarding their intention with respect to further follow-up assessments on study. Consent withdrawn means that the patient has explicitly indicated that he or she no longer wants to be followed; in this case no further data, except data in the public domain, may be solicited from or collected on the patient.
- Unacceptable AEs or failure to tolerate study treatment as defined as:
 - Grade 4 or life-threatening AE;
 - Toxicity requiring more than the allowed number of dose reductions for encorafenib and binimetinib as described in [Table 8](#);

- Occurrence of an AE that is related to study treatment and in the judgment of the Investigator compromises the patient's ability to continue study-specific procedures, or is considered to not be in the patient's best interest;
- Missing > 28 consecutive days of dosing with treatment, unless, in the opinion of the Investigator and in consultation with the Sponsor Medical Monitor, the patient will derive clinical benefit from continued treatment.
- Clinical progression, as determined by the Investigator in the absence of radiographic progression as defined by RECIST v1.1.
- Disease progression per both mRECIST v1.1 for brain metastasis and RECIST v1.1 for extracranial disease. If there is progression in either brain metastasis or extracranial disease (not both compartments), the patient may continue treatment if, in the opinion of the Investigator, the patient is deriving clinical benefit.
- Patient becomes pregnant or begins breastfeeding.
- Significant protocol deviation that, in the opinion of the Investigator or Sponsor, renders the patient unsuitable for further study treatment administration.
- Patient noncompliance with study procedures that, in the judgment of the Investigator or Sponsor, renders the patient unsuitable for further study participation.
- Lost to follow up.
- Death.
- Termination of the study by the Sponsor (described in [Section 9.10](#)).

Note that patients who discontinue study treatment may participate in treatment discontinuation assessments at the EOT visit, if applicable, as outlined in the SoA ([Table 3](#)). The date of the last dose of study treatment will be recorded in the eCRF. See the SoA for data to be collected at the time of treatment discontinuation and follow up.

Patients will have the option to stop receiving study treatment and continue in the Follow-up Period of the study for safety/efficacy assessments. If the patient discontinues study treatment and actively withdraws consent for collection of follow-up data (safety follow up and disease assessments), no additional data collection will occur.

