If a patient misses > 28 consecutive days of dosing with combination treatment (both encorafenib and binimetinib), study treatment will be discontinued unless, in the opinion of the Investigator, the patient will derive clinical benefit from continued treatment. The Investigator will discuss this decision with the Sponsor Medical Monitor. If a patient permanently discontinues binimetinib (i.e., no dose for > 28 days), the patient may continue single-agent encorafenib if, in the opinion of the Investigator, the patient is deriving clinical benefit. Doses of single-agent encorafenib are decreased to a maximum of 300 mg QD when binimetinib is permanently discontinued.

If a patient permanently discontinues treatment with encorafenib, he or she must discontinue treatment with binimetinib.

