Appendix 2. Recommended Dose Modifications for Encorafenib-related* Adverse Events

Severity of Adverse Event	Dose Modifications
New Primary Malignancies	
Non-cutaneous RAS mutation-positive malignancies	Permanently discontinue.
Uveitis	
Grade 1-3	If Grade 1 or 2 does not respond to specific ocular therapy, or for Grade 3 uveitis, withhold encorafenib and binimetinib for up to 6 weeks. 
 • If improved, resume at same or reduced dose. • If not improved, permanently discontinue.
Grade 4	Permanently discontinue encorafenib and binimetinib.
Other Eye Disorders (i.e., non-Uveitis Events)	
Grade 1–2	Maintain dose level of encorafenib and binimetinib and increase frequency of ophthalmic monitoring to at least every 14 days until stabilization or resolution.
Grade 3	Interrupt dosing of encorafenib and binimetinib and refer patient to ophthalmologist within 7 days. 
 1. If resolved to Grade ≤ 1 in ≤ 21 days, resume treatment at 1 reduced dose level of encorafenib and binimetinib. 2. If not resolved to Grade ≤ 1 in ≤ 21 days, permanently discontinue encorafenib and binimetinib and close follow-up with ophthalmic monitoring until stabilization or resolution.
Grade 4	Permanently discontinue encorafenib and binimetinib and immediate follow-up with ophthalmic monitoring until stabilization or resolution.
QTc Prolongation	
QTcF > 500 ms and ≤ 60 ms increase from baseline	1 st occurrence: 
 • Temporarily interrupt dosing of encorafenib until QTcF < 500 ms. Then resume treatment at 1 reduced dose level of encorafenib. 2 nd occurrence: 
 • Temporarily interrupt dosing of encorafenib treatment until QTcF < 500 ms. Then resume treatment at 1 reduced dose level of encorafenib. 3 rd occurrence: 
 • Permanently discontinue encorafenib.
QTcF > 500 ms and > 60 ms increase from baseline	Permanently discontinue.

Severity of Adverse Event	Dose Modifications
Hepatotoxicity	
Grade 2 AST or ALT increased	Maintain encorafenib dose. 
 If no improvement within 4 weeks, withhold encorafenib until improved to Grade 0-1 or to pretreatment/baseline levels and then resume at the same dose.
Grade 3 or 4 AST or ALT increased	See Other Adverse Reactions
Dermatologic (Except Hand-foot Skin Reactions)	

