Grade 3	
Interrupt dosing of encorafenib and binimetinib until resolved to Grade ≤ 1. Then resume treatment at 1 reduced dose level of encorafenib. Resume treatment with binimetinib at the current dose if, in the judgment of the Investigator, the toxicity is considered to be unrelated to binimetinib, or at 1 reduced dose level.
 
Note: Interrupt dosing of encorafenib and binimetinib for ≥ Grade 3 vomiting or Grade 3 nausea only if the vomiting or nausea cannot be controlled with optimal antiemetics (as per local practice).

Grade 4	Permanently discontinue encorafenib and binimetinib.
Other Adverse Reactions (including renal, haemorrhage). Additional renal guidance is provided in Section 7.3.9.	
Recurrent Grade 2 or First occurrence of any Grade 3	
Withhold for up to 4 weeks.
 
 If improves to Grade 0-1 or to pretreatment/baseline levels, resume at reduced dose. If no improvement, permanently discontinue.

Severity of Adverse Event	Dose Modifications
First occurrence of any Grade 4	Permanently discontinue or withhold for up to 4 weeks. 
• If improves to Grade 0-1 or to pretreatment/baseline levels, then resume at a reduced dose.• If no improvement, permanently discontinue.
Recurrent Grade 3	Consider permanently discontinuing.
Recurrent Grade 4	Permanently discontinue.

*For adverse events that may be related to both encorafenib and binimetinib, guidance is provided for the other agent also.

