	
 If resolved to Grade ≤ 1 in ≤ 21 days, resume treatment at 1 reduced dose level of encorafenib and binimetinib. If not resolved to Grade ≤ 1 in ≤ 21 days, permanently discontinue encorafenib and binimetinib and close follow-up with ophthalmic monitoring until stabilization or resolution.
Grade 4	Permanently discontinue encorafenib and binimetinib and immediate follow-up with ophthalmic monitoring until stabilization or resolution.
Interstitial Lung Disease	
Grade 2	Withhold binimetinib for up to 4 weeks. 
 If improved to Grade 0-1, resume at a reduced dose. If not resolved within 4 weeks, permanently discontinue.
Grade 3 or Grade 4	Permanently discontinue.
Hepatotoxicity	
Grade 2 AST or ALT increased	Maintain binimetinib dose. 
 If no improvement within 2 weeks, withhold binimetinib until improved to Grade 0-1 or to pretreatment/baseline levels and then resume at the same dose.
Grade 3 or 4 AST or ALT increased	See Other Adverse Reactions
Rhabdomyolysis or Creatine Phosphokinase (CPK) elevations	
Grade 4 asymptomatic CPK elevation or Any Grade CPK elevation with symptoms or with renal impairment	Withhold binimetinib dose for up to 4 weeks. 
 If improved to Grade 0-1 resume at a reduced dose. If not resolved within 4 weeks, permanently discontinue binimetinib.
Dermatologic	
Grade 2	If no improvement within 2 weeks, withhold until Grade 0-1. Resume at same dose if first occurrence or reduce dose if recurrent.
Grade 3	Withhold until Grade 0-1. Resume at same dose if first occurrence or reduce dose if recurrent.
Grade 4	Permanently discontinue.
Nausea/Vomiting	
Grade 1-2	Maintain dose level of encorafenib and binimetinib. Promptly institute antiemetic measure.
Grade 3	Interrupt dosing of encorafenib and binimetinib until resolved to Grade ≤ 1 . Then resume treatment at 1 reduced dose level of encorafenib. Resume treatment with binimetinib at the current dose if, in the judgment of the Investigator, the toxicity is considered to be unrelated to binimetinib, or at 1 reduced dose level.

Severity of Adverse Event	Dose Modifications
	Note: Interrupt dosing of encorafenib and binimetinib for \geq Grade 3 vomiting or Grade 3 nausea only if the vomiting or nausea cannot be controlled with optimal antiemetics (as per local practice).
Grade 4	Permanently discontinue encorafenib and binimetinib.

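### Protocol Section 6.8 stops study treatment for any Grade 4 adverse event, while Appendices 2 and 3 let some first Grade 4 events be held and resumed, and no text says which governs

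*Protocol*

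**What the plan says.** **Section 6.8** opens its list with "Patients meeting any of the following criteria should discontinue study treatment". Under unacceptable or untolerated adverse events it includes "Grade 4 or life-threatening AE". That item is not limited to related, recurrent or unresolved events.

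**Appendices 2 and 3** (encorafenib and binimetinib) each end with a residual category, Other Adverse Reactions. For a first Grade 4 event there, both say "Permanently discontinue or withhold for up to 4 weeks". Treatment may restart at a reduced dose once the event has recovered to Grade 0-1 or baseline, and stops if it has not improved. Both hepatotoxicity blocks send Grade 3 or 4 AST or ALT to this category. Appendix 3 also has a row for "Grade 4 asymptomatic CPK elevation": binimetinib is held for up to 4 weeks, resumed at a lower dose if improved, and stopped only if unresolved.

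**Missed doses.** Section 6.8 also lists "Missing > 28 consecutive days of dosing with treatment", with an exception where the Investigator, having consulted the Medical Monitor, expects continuing to help. Section 6.7.1 has the matching rule for both drugs: "study treatment will be discontinued unless, in the opinion of the Investigator, the patient will derive clinical benefit from continued treatment". Section 6.7.1 also describes permanent binimetinib discontinuation as a gap in dosing of more than 28 days. The Appendix 2 uveitis row says to "withhold encorafenib and binimetinib for up to 6 weeks" in the cases it covers, then to resume if improved. Appendix 3 has the same hold for both drugs.

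**The concern.** A stopping rule and a hold-and-resume rule are both written for the same event. An investigator with a first treatment-related Grade 4 ALT result finds an instruction to stop in the body of the protocol and permission to hold and restart in the appendices. Neither place refers to the other on this point.

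Two things are at stake. The first is patient safety, because whether a patient is re-exposed after a Grade 4 event can depend on which page the site reads. The second is the meaning of the discontinuation counts. Discontinuations due to adverse events are part of the primary Safety Lead-in endpoint (Protocol Section 3, Table 4). SAP Section 6.6.1 tabulates events leading to interruption, reduction and permanent discontinuation by drug, and again for patients escalated to 600 mg. The same clinical event falls in the discontinuation table at one site and in the interruption and reduction tables at another.

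**Working it through.** The plan states no figure to reproduce here. The check sets the texts side by side and adds one conversion of weeks to days.

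**Step 1. Grade 4 events**

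| Event | Section 6.8 | Appendix 2 or 3 | Agree? |
|---|---|---|---|
| First Grade 4 event in the residual category | Stop study treatment | Stop, or hold up to 4 weeks and resume lower | No |
| Grade 4 AST or ALT | Stop study treatment | Sent to the residual category, so as above | No |
| Grade 4 asymptomatic CPK elevation | Stop study treatment | Hold binimetinib up to 4 weeks and resume lower; stop it only if unresolved | No |
| Grade 4 uveitis, other eye, dermatologic, nausea/vomiting | Stop study treatment | Stop permanently | Yes, at least for the drug the row covers |

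The conflict is therefore confined to particular rows. The appendices also have a separate row for recurrent Grade 4 events, which calls for permanent discontinuation. That row has work to do only if a patient can still be on treatment after a first Grade 4 event, so the appendices plainly contemplate continuation. Section 6.8 as worded does not.

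**Step 2. Is there a tie-breaker?**

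- Section 6.7.1 calls for clinical judgment, in consultation with the Sponsor Medical Monitor, on interruptions and modifications. It does not mention the Section 6.8 criteria.
- Its allowance for transient laboratory abnormalities is an exemption from dose-reduction rules, not from stopping criteria.
- The appendices are headed as recommendations, and Section 6.8 is phrased with *should*. Neither is ranked above the other.
- Section 7 says that waivers and exemptions are not allowed.

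No precedence is stated.

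**Step 3. Missed days**

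- Uveitis hold: 6 × 7 = 42 days, and 42 − 28 = 14 days beyond the limit in Sections 6.7.1 and 6.8.
- Holds capped at 4 weeks: 4 × 7 = 28 days, which is not more than 28, so a hold that ends on time does not trigger the rule.

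Uveitis is the only event with a stated hold longer than 28 days. From day 29 to day 42 the row allows resumption without mentioning the limit, its exception or the consultation. Over the same days, the Section 6.7.1 description would class binimetinib as permanently discontinued.

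**Step 4. How many patients?**

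Section 2.2.3 gives Grade 3 and 4 combined for laboratory abnormalities (ALT 6%, CPK 5%), with no overall Grade 4 rate for encorafenib plus binimetinib. The 5% Grade 4 figure in Section 2.1.3 belongs to dabrafenib plus trametinib. The 4.4% for uveitis is overall incidence, whereas only Grade 3 cases, or Grade 1-2 cases that do not respond to ocular therapy, are held. None of these yields a count of patients exposed to the conflict.

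**The case against.** The strongest reply is that discretion is intended. The residual Grade 4 row itself offers stopping or holding, so sites could differ under the appendices alone, and a site that stops complies with both texts. Consultation with the Medical Monitor should also pull decisions together. This stands in part and makes divergence less likely. It does not remove the conflict: a site that holds and resumes follows the appendix and departs from Section 6.8. For Grade 4 asymptomatic CPK elevation the row prescribes a hold first, so stopping at onset departs from the row.

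A reader might infer that the 6-week uveitis hold flatly contradicts the 28-day rule. The documents do not support that. Sections 6.7.1 and 6.8 both allow treatment to continue beyond 28 days when benefit is expected, with the Medical Monitor involved, and Section 6.7.1 asks for Medical Monitor contact before restarting after any delay of more than 14 days. A site can hold for 6 weeks, consult and resume within all the texts, apart from the description of permanent binimetinib discontinuation.

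A reader might also infer that early stopping costs responses and so moves the primary endpoint. That would rest on Protocol Appendix 5, which ignores scans more than 30 days after the last dose. The best-response rule in SAP Section 6.1.2 has no such limit, and Protocol Section 7.2.4.2 keeps imaging patients every 8 weeks if they stop without progression. A response would be lost only if the event came before confirmation and no qualifying scan followed. The documents give no basis for counting such patients.

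**Conclusion.** The Grade 4 inconsistency holds and should be corrected. Section 6.8 and the two appendices give different stop or continue outcomes for a first Grade 4 event in the residual category, for Grade 4 AST or ALT, and for Grade 4 asymptomatic CPK elevation, and nothing states which prevails. The consequence is for patient safety and for the interpretation of the adverse-event discontinuation tables. The number of patients affected is unknown. No effect is claimed on the brain metastasis response rate, the sample size or the test. The uveitis point is lesser: a missing cross-reference, plus a description of permanent binimetinib discontinuation that sits awkwardly with a 42-day hold. The conclusion rests on reading the documents as they stand and assumes that no other study document available to sites settles the precedence.

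**What to change.** Reconcile Sections 6.7.1 and 6.8 with Appendices 2 and 3 so that one rule applies to each Grade 4 event, or add a sentence stating which text governs when they differ. Add a cross-reference between the uveitis rows in both appendices and the 28-day rule with its exception, and make clear how the description of permanent binimetinib discontinuation in Section 6.7.1 applies during such a hold. Which clinical rule stands is for the clinical team, and this review takes no view on it. The cost is clarifying wording in a protocol amendment and notice to sites, with no added procedures.

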6.9. Patient Discontinuation/Withdrawal from the Study

- A patient may withdraw from the study at any time at his/her own request or may be withdrawn at any time at the discretion of the Investigator for safety, behavioral, compliance or administrative reasons. This is expected to be uncommon.
- See the SoA ([Table 3](#)) for data to be collected at the time of study discontinuation and follow up and for any further evaluations that need to be completed.
- If the patient withdraws consent for disclosure of future information, the Sponsor may retain and continue to use any data collected before such a withdrawal of consent.
- If a patient withdraws from the study, he/she may request destruction of any samples taken and not tested, and the Investigator must document this in the site study records.

6.10. Intervention After the End of the Study

At the end of the study, access to study treatment will be provided, in accordance with applicable regulations and requirements, to all patients who are continuing to benefit from study treatment. Where required by local regulations, this protocol may be amended to allow patients to continue treatment, and re-consent of ongoing patients will be required.

The Sponsor will notify all applicable regulatory agencies in accordance with local requirements when the study has ended. In such cases, appropriate safety information will continue to be captured per protocol and submitted to the Sponsor. The information to be collected includes treatment-related AEs and SAEs, laboratory results of special interest, study treatment administration, patient status and date and reason(s) for study withdrawal.

6.11. Replacement of Patients

Patients may be replaced for any of the following reasons:

- During the Safety Lead-in, any patient who receives < 75% of the planned cumulative dose of either encorafenib or binimetinib during Cycle 1 for any reason other than a DLT (e.g., not evaluable for a DLT [Table 7]) may be replaced to ensure a minimum number of evaluable patients.
- Patients who do not meet the eligibility requirements of the study may be replaced.
- Patients for whom the *BRAFV600* mutation status is not confirmed by central laboratory may be replaced. This includes either an Indeterminate or a No Mutation *BRAFV600* Detected result.

6.12. Lost to Follow up

A patient will be considered lost to follow up if he or she repeatedly fails to return for scheduled visits and is unable to be contacted by the study site.

The following actions must be taken if a patient fails to return to the clinic for a required study visit:

- The site must attempt to contact the patient and reschedule the missed visit as soon as possible and counsel the patient on the importance of maintaining the assigned visit schedule and ascertain whether or not the patient wishes to and/or should continue in the study.
- Before a patient is deemed lost to follow up, the Investigator or designee must make every effort to regain contact with the patient. These contact attempts will be documented in the patient's medical record.
- Should the patient be unreachable, he/she will be considered to have withdrawn from the study and lost to follow up.

